5.2. Discontinuation from the Study

Subjects may be discontinued from the study at any time for any of the following reasons:

- Withdrawal by subject or parent/guardian
- Deviation/noncompliance with the study protocol that in the judgement of the Investigator and/or Medical Monitor the subject should not continue study treatment
- Study termination by Sponsor
- Lost to follow-up
- Death
- Other

A subject may withdraw from the study at any time for any reason without prejudice to their future medical care by the physician or at the institution. If a subject withdraws consent, no further evaluation should be performed, and no additional data should be collected. The Sponsor may retain and continue to use any data collected before such withdrawal of consent. The Investigator should make a reasonable attempt to document the specific reason why consent was withdrawn.

In the event that a subject fails to attend any follow-up visits, all reasonable efforts will be made to contact the subject to ensure that he/she is in satisfactory health. All contacts and contact attempts must be documented in the subject's file.

5.3. Subjects Lost to Follow-Up Prior to Last Scheduled Visit

A subject will be considered lost to follow-up if he or she repeatedly fails to return for scheduled visits and is unable to be contacted by the study site.

The following actions must be taken if a subject fails to attend a required onsite, offsite, virtual, or hybrid visit:

- The site must attempt to contact the subject and reschedule the missed visit as soon as possible and counsel the subject on the importance of maintaining the assigned visit schedule and ascertain whether or not the subject wishes to and or should continue in the study.
- Before a subject is deemed lost to follow-up, the Investigator or designee must make every effort to regain contact with the subject (where possible, 3 telephone calls and if necessary, a certified letter to the subject's last known mailing address or local equivalent methods). These contact attempts should be documented in the subject's file.

Should the subject continue to be unreachable, he/she will be considered to have withdrawn from the study.

5.4. Premature Termination of the Study

The Sponsor has the right to terminate this study at any time. Reasons for terminating the study may include, but are not limited to, the following:

- The incidence or severity of adverse events in this or other studies indicates a potential health hazard to subjects
- Subject enrollment is unsatisfactory
- Upon request of health authorities

The Sponsor will notify Investigators if the study is placed on hold or if the Sponsor decides to discontinue the study or development program. Health authorities and IECs/IRBs will be informed about the termination of the study in accordance with applicable regulations.

The Sponsor has the right to replace a study site at any time. Reasons for replacing a study site may include, but are not limited to:

- Excessively slow recruitment
- Poor protocol adherence
- Inaccurate or incomplete data recording
- Non-compliance with the International Council for Harmonisation (ICH) guideline for Good Clinical Practice (GCP).

6. STUDY TREATMENTS

6.1. Treatments Administered

Subjects will be randomly assigned to 1 of 2 treatment groups (etrasimod or placebo) in a 2:1 ratio. Study treatment is outlined in [Table 1](#).

Table 1: Study Treatment

| | | |
|----------------------------------|-------------------------------------------------------------------------------------------------------------------------------------------------------------------------------------------------------------------------------------------------------------|-------------------------------------------------------------------------------------------------------------------------------------------------------------------------------------------------------------------------------------------------------------|
| Study treatment name: | Etrasimod | Placebo |
| Dosage formulation: | 2 mg tablet | Matching tablet |
| Unit dose strength/dosage level: | 1 tablet once daily | 1 tablet once daily |
| Route of administration: | By mouth | By mouth |
| Packaging and labeling: | Study treatment will be provided in 40 cc, induction-sealed, high-density polyethylene bottles with child-resistant screw caps. Each bottle will be labeled as required per country requirement. These bottles should be stored at 15 to 25°C (59 to 77°F). | Study treatment will be provided in 40 cc, induction-sealed, high-density polyethylene bottles with child-resistant screw caps. Each bottle will be labeled as required per country requirement. These bottles should be stored at 15 to 25°C (59 to 77°F). |

6.2. Investigational Study Treatment

The active pharmaceutical ingredient in etrasimod tablets is APD334 [REDACTED]

[REDACTED]. APD334 [REDACTED] is manufactured, packaged, tested, and released in compliance with cGMP.

The drug product is a blue, round, biconvex, plain, immediate-release, film-coated tablet. Etrasimod tablets are supplied in the dosage strength (based on etrasimod free acid content) of 2 mg.

The placebo tablet formulation is composed of excipients [REDACTED]

[REDACTED]. Placebo tablets are identical in appearance to the active-drug tablets as described above.

6.3. Dosage and Administration

One tablet is to be taken each day (with water, either with or without food). Tablets should be taken at approximately the same time each day, preferably in the morning. On study visit days, subjects should wait and take their dose at the study site after blood draws for PK and after all pre-dose assessments and procedures have been completed. The time of PK sample collection and last dosing prior to the PK sample should be documented in the eCRF.

6.3.1. Instructions for Missed Dose(s)

Subjects should be instructed that if they forget to take a dose, they can take the dose within 8 hours of the normal dosing time; otherwise, they should take their next dose at the regular time on the following day. If the subject vomits the tablet, he/she should be instructed not to take another tablet on the same day, but to take the next dose at the regular time on the following day. Missed doses should be recorded in the subject's electronic diary (eDiary), as indicated in the Schedule of Assessments, [Table 7](#) and [Table 8](#). Subjects should be instructed to contact the Investigator if they miss more than 2 consecutive doses.

Subjects who do not take the study treatment for ≥ 2 consecutive days within the first week of treatment or for ≥ 7 consecutive days after the first week of treatment must contact the Investigator to discuss treatment re-initiation. The subject must take the next dose of study treatment at the study site, and the in-clinic cardiac monitoring as outlined in Section 9.4.2.1 should be performed.

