6.3.2. Dose Interruptions

If the Investigator deems it necessary to withhold study treatment, temporary withholding is permitted for up to 6 days without obtaining prior approval from the Medical Monitor. If study treatment interruption ≥ 7 days is required for a medical reason, the Investigator must contact the Medical Monitor.

The first-dose monitoring as outlined in Section 9.4.2.1 should be performed any time a subject misses study treatment as follows:

- ≥ 2 consecutive days within the first week of treatment, or
- ≥ 7 consecutive days after the first week of treatment

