6.7.3. Prohibited Concomitant Therapy

The following concomitant medications are prohibited during the study:

- Treatments for UC other than those listed in Section 6.7.2.1 (either approved or investigational)
- All live vaccines, during study treatment and within 8 weeks after the last dose of study treatment
- Moderate/strong inhibitors or inducers of CYP2C8 and CYP2C9 (Table 2; for additional information, refer to (Flockhart 2019))

Table 2: Cytochrome P450 Inhibitors and Inducers

| Cytochrome P450 | Inhibitors (Strong/Moderate) | Inducers (Strong/Moderate) |
|-----------------|----------------------------------------------------------|--------------------------------------------------------------|
| CYP2C8 | Clopidogrel, gemfibrozil, deferasirox, teriflunomide | Rifampin |
| CYP2C9 | Fluconazole, amiodarone, felbamate, miconazole, piperine | Aprepitant, carbamazepine, enzalutamide, rifampin, ritonavir |

CYP, cytochrome P450

- Start, stop, or change in dosage of any anti-arrhythmic drugs (Class I to IV) within 1 week before or after treatment re-initiation following drug interruption as specified in Section 6.3.2
- Inhibitors of UGT1A7
- Chronic nonsteroidal anti-inflammatory drugs (NSAID) use (Note: Occasional use of NSAIDs and acetaminophen [eg, headache, arthritis, myalgias, or menstrual cramps] and aspirin up to 325 mg/day is permitted)
- Marketed biologic therapies
- Immunosuppressive agents (eg, AZA, 6-MP, tofacitinib)
- Any per rectum therapy including enemas (eg, 5-ASA, corticosteroid), other than that required for endoscopy preparation
- Cyclosporine, tacrolimus, sirolimus, methotrexate, or MMF
- Cholestyramine or other drugs interfering with enterohepatic circulation, unless the treatment has been stable for > 6 months prior to screening
- Any investigational drug other than the study treatment
- Treatment with D-penicillamine, thalidomide, dimethyl fumarate, or pyrimidine synthesis inhibitors
- Treatment with lymphocyte-trafficking inhibitors (natalizumab, fingolimod, siponimod, ozanimod)
- Immunosuppressive agents that deplete lymphocytes (eg, alemtuzumab, anti-CD4, cladribine, rituximab, ocrelizumab, cyclophosphamide, mitoxantrone, daclizumab)

The following concomitant procedures are prohibited during the study:

- Major elective surgery
- Immunoabsorption columns
- Intravenous immunoglobulin or plasmapheresis
- Blood donations during the study and for 14 days after the last dose of study treatment.

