9.4.2.1. Guidance for Cardiac Monitoring Following Treatment Initiation or Re-Initiation

Prerandomization (ie, pre-dose/baseline) vital signs (resting heart rate, systolic and diastolic BP, body temperature, and respiratory rate) will be used as the Baseline measurement. The pre-dose heart rate measurement will be used for comparison to the post-dose measurement. Subjects should receive the first dose of study treatment before 12:00 PM (noon).

First Dose Cardiac Monitoring

In-clinic cardiac monitoring, of at least 4 hours, will occur on Day 1 and will include the following ([Table 3](#)):

- Full baseline vital signs (heart rate, systolic and diastolic BP, body temperature, and respiratory rate) and a 12-lead ECG (taken with the subject in the supine position) will be assessed prerandomization.
- After the first dose of study treatment on Day 1, subjects must remain under observation in the clinic for at least 4 hours.
- At Hours 1, 2, and 3 (\pm 15 minutes) post-dose, the heart rate and systolic and diastolic BP will be assessed with the subject in the sitting position, with the time recorded. If the subject has a heart rate $<$ 50 bpm or if cardiovascular symptoms develop, then the subject should remain closely monitored, including 12-lead ECGs as clinically indicated, until the Hour 4 discharge assessment.
- At the Hour 4 (\pm 15 minutes) discharge assessment, heart rate and systolic and diastolic BP will be assessed with the subject in the sitting position and a 12-lead ECG (with the subject in the supine position) will be performed. Subjects may be discharged from the clinic after the 4-hour assessment if they meet the criteria

described in [Table 4](#). Subjects not meeting the discharge criteria will require extended monitoring as described below.

- Subjects experiencing a clinically relevant treatment-related symptomatic event (eg, chest pain, dizziness, palpitations, or syncope) associated with reduction of the heart rate or clinically relevant 12-lead ECG changes at any time during the 4-hour monitoring period must be discontinued from treatment ([Table 5](#)).

Table 3: Procedures to be Performed During the Monitoring Period

| Procedure | Pre-Dose | Hours 1, 2, 3 Post-Dose ^a | Hour 4 Post-Dose ^a |
|--------------------------------------------|----------|--------------------------------------|-------------------------------|
| Blood pressure and heart rate ^b | x | x | x |
| 12-lead ECG | x | | x |
| Assess discharge criteria | | | x |

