^a Measurements may be taken \pm 15 minutes of the scheduled time.

^b Heart rate is based on vital signs.

Table 4: Discharge Criteria After Cardiac Monitoring

| |
|--------------------------------------------------------------------------------------------------------------------------------------------------------------------------|
| Subjects will be released from the clinical site after dosing on Day 1 (but no sooner than 4 hours post-dose) when they fulfill the following discharge criteria: |
| 
 • Heart rate \geq 50 bpm or no more than 10 bpm lower than the pre-dose (baseline) value |
| 
 • No evidence of second-degree AV block or higher |
| 
 • No cardiac symptoms (eg, chest pain, dizziness, palpitations, lightheadedness, shortness of breath, or syncope) |

AV, atrioventricular

Note: Subjects should have written instructions on when to return to the clinic and a 24-hour contact phone number to call in the event of any new or worsened cardiovascular symptoms.

Extended Cardiac Monitoring

Subjects who do not meet discharge criteria at 4-hours post-dose will require extended cardiac monitoring:

- Vital signs will be assessed hourly and 12-lead ECG may be performed, as clinically indicated, until the subject meets the discharge criteria ([Table 4](#)).
- The Medical Monitor should be contacted if the subject does not meet the discharge criteria after \geq 4 hours of extended cardiac monitoring.
- Any subject who requires extended monitoring on Day 1 must return on Day 2 for the second dose and will be re-monitored as on Day 1. These subjects will be discontinued from study treatment if they do not meet the discharge criteria at 4 hours after the second dose. Extended cardiac monitoring should be continued until the subject meets the discharge criteria ([Table 4](#)).
- Subjects experiencing a symptomatic event (eg, chest pain, dizziness, palpitations, lightheadedness, shortness of breath, or syncope) at any time during the 4-hour monitoring period that is not associated with either a reduction in heart rate or clinically relevant change in 12-lead ECG, may be discharged provided they meet the

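### In week 1, the instruction on when subjects should call about missed doses triggers one dose later than the protocol's own threshold for a monitored restart

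*Protocol*

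**What the plan says.** Section 6.3 sets once-daily dosing: "One tablet is to be taken each day".

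Section 6.3.1 then gives two contact rules. The first paragraph covers what to do about a forgotten or vomited tablet and ends with the advice to be passed to subjects: "Subjects should be instructed to contact the Investigator if they miss more than 2 consecutive doses". The second paragraph sets a firmer rule with two limits: 2 or more days in a row without treatment in the first week, or 7 or more later. Subjects who reach the later limit, "consecutive days after the first week of treatment must contact the Investigator to discuss treatment re-initiation", and those who reach the first-week limit have the same duty. It continues: "The subject must take the next dose of study treatment at the study site", with the in-clinic cardiac monitoring of Section 9.4.2.1.

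The same two limits appear in Section 6.3.2 ("The first-dose monitoring as outlined in Section 9.4.2.1 should be performed any time a subject misses study treatment as follows"), in the re-initiation part of Section 9.4.2.1, and in Table 8 footnote e.

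**The concern.** Section 6.3.1 uses two numbers for when a subject should call in week 1. The sentence worded as an instruction to subjects has the later one. A subject told only the first paragraph would not call after two missed doses. The advice there for a dose missed beyond the 8-hour window is to resume at the usual time on the following day, which in practice means at home. The second paragraph requires that same dose to be taken on site.

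The stake is first-dose cardiac safety. Section 1.3 lists first-dose bradycardia and AV block among the events reported with S1P receptor modulators, and the protocol requires first-dose monitoring to be repeated after such a gap. Section 6.7.3 also bars starting, stopping or changing the dose of anti-arrhythmic drugs "within 1 week before or after treatment re-initiation following drug interruption as specified in Section 6.3.2". The site can apply these safeguards at the restart only if it knows of the gap beforehand.

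**Working it through.** No sample size, power or error rate is involved. The check compares integer thresholds and then looks at the visit calendar.

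**Inputs**
- Dosing: 1 tablet a day (Section 6.3), so 1 missed dose = 1 missed day.
- Call threshold, first paragraph of 6.3.1: more than 2 doses.
- Monitored-restart threshold in week 1: 2 or more days (6.3.1 second paragraph, 6.3.2, 9.4.2.1). After week 1: 7 or more days.
- Week 2 visit: Day 15 ± 3 (Section 9.4.2, Table 7).
- Monitoring content: Section 9.4.2.1 ("In-clinic cardiac monitoring, of at least 4 hours, will occur on Day 1") and Table 3.

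**Thresholds**

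| Period | Call sentence triggers at | Monitored restart triggers at | Order |
|---|---|---|---|
| Week 1 | 3 doses = 3 days | 2 days | call is 3 − 2 = 1 dose late |
| After week 1 | 3 doses = 3 days | 7 days | call is 7 − 3 = 4 days early |

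The only uncovered case is exactly 2 consecutive missed doses in week 1.

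**Would a scheduled contact catch it?** Take week 1 as Days 1 to 7, with the Day 1 dose given in clinic. The possible two-day gaps are Days 2–3, 3–4, 4–5, 5–6 and 6–7, which is 5 gaps, with restarts on Days 4, 5, 6, 7 and 8. The earliest Week 2 visit is Day 15 − 3 = Day 12. The restarts precede it by 12 − 4 = 8, 7, 6, 5 and 12 − 8 = 4 days. All 5 restarts therefore come before the next scheduled visit. Missed doses are recorded in the eDiary, but the stated site review of the eDiary is at treatment visits (Table 7 footnote g), so that review comes after the restart. A subject recalled on Day 2 for re-monitoring takes that dose in clinic, which removes the Days 2–3 gap and leaves 4.

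**What an unmonitored restart would omit (Table 3).** One observation period of at least 4 hours, with heart rate and blood pressure at pre-dose and Hours 1, 2, 3 and 4 (1 + 4 = 5 readings) and a 12-lead ECG at pre-dose and Hour 4 (2 ECGs).

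**Other prompts**
- The Table 4 note says "Subjects should have written instructions on when to return to the clinic and a 24-hour contact phone number", but ties this to new or worsened cardiovascular symptoms, not to missed doses.
- The re-monitoring footnote is in Table 8, which covers Weeks 16 to 52. Table 7 covers week 1; its footnotes k and m cite Section 9.4.2.1 for Day 1, and it has no re-initiation footnote.

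**The case against.** The strongest reply is that the safeguard is already in the section. The second paragraph of 6.3.1 is specific to the first week, uses mandatory language and puts the duty on the subject, who can meet it only if told of it. Both paragraphs sit under a heading about instructions for missed doses, and Section 6.6 makes the Investigator responsible for instructing subjects correctly. Read this way, the first paragraph is general advice about a single forgotten tablet, and nothing in it authorises an unmonitored restart. The 2-day limit is consistent wherever monitoring is specified, Section 9.10.3 ties all ECGs to Section 9.4.2.1, and SAP Section 6.4 provides analysis visits for cardiac re-monitoring. Any harm depends on subject materials that cannot be seen, and counting calendar gaps is not a risk estimate.

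Most of this stands. The paragraphs do not strictly contradict each other, the correct rule is present, and no frequency of unmonitored restarts can be given. The Table 7 footnote and the count of five gaps are secondary. What remains is that the protocol states an explicit call threshold for subjects, and in week 1 that threshold is one dose later than the one that matters. In that week the site would normally learn of the gap only if the subject calls, so the number the subject is given is operative.

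**Conclusion.** The point holds on narrow terms. In week 1 the subject-facing call threshold is one dose too late for the protocol's own monitored-restart rule. It affects only subjects who miss exactly 2 consecutive doses in that week. After week 1 the thresholds are in a safe order.

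The comparison of thresholds needs only the once-daily schedule. The calendar result also assumes that week 1 means Days 1 to 7 and that no unscheduled contact takes place. The documents do not say how often such gaps occur or what subject materials tell subjects. If those materials already carry the second paragraph's rule, the practical gap closes. This is a low-severity wording correction with a patient-safety rationale. It does not bear on any endpoint, estimand or analysis.

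**What to change.** Replace the last sentence of the first paragraph of Section 6.3.1 with:

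> *During the first week of treatment, subjects should be told to contact the Investigator before taking any further tablet if they miss 2 or more doses in a row. After the first week, they should be told to make contact if they miss more than 2 doses in a row.*

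Use the same wording in subject materials. Optionally, repeat the re-monitoring sentence of Table 8 footnote e in Table 7, since that schedule covers week 1.

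With this change the week 1 call triggers at 2 missed doses, so the gap to the monitored-restart threshold falls from 1 dose to 0, and the later rule is unchanged. The cost is one protocol sentence, matching text in subject materials and, if wanted, one repeated footnote. It introduces no new policy.

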6.3.2. Dose Interruptions

If the Investigator deems it necessary to withhold study treatment, temporary withholding is permitted for up to 6 days without obtaining prior approval from the Medical Monitor. If study treatment interruption ≥ 7 days is required for a medical reason, the Investigator must contact the Medical Monitor.

The first-dose monitoring as outlined in Section 9.4.2.1 should be performed any time a subject misses study treatment as follows:

- ≥ 2 consecutive days within the first week of treatment, or
- ≥ 7 consecutive days after the first week of treatment

6.4. Method of Assigning Subjects to Treatment

Subjects will be centrally assigned to randomized study treatment using an Interactive Web Response System (IWRS). Before the study is initiated, the log in information and directions for the IWRS will be provided to each study site.

Subjects will be randomized to study treatment via stratified randomization. Randomization will be stratified by (a) naïve to biologic or JAK inhibitor therapy at study entry (yes or no), (b) baseline corticosteroid use (yes or no), and (c) baseline disease activity (MMS: 4 to 6 or 7 to 9).

Each subject will be dispensed blinded study treatment at study visits (Table 7 and Table 8).

6.5. Blinding

This is a double-blind study with limited access to the randomization code. The study treatment and placebo tablets and bottles are identical in physical appearance. The treatment each subject receives will not be disclosed to the Investigator, study site staff, subject, Sponsor personnel involved with the conduct of the study (with the exception of the clinical supply staff and designated safety staff), or study vendors. The IWRS will hold treatment codes and bottle numbers for study treatment.

Treatment assignments should remain blinded unless that knowledge is necessary to determine subject emergency medical care. In case of an emergency, the Investigator has the sole responsibility for determining if unblinding of a subject's treatment assignment is warranted to provide appropriate medical care. Subject safety must always be the first consideration in making such a determination. The IWRS is programmed with blind-breaking instructions to guide the Investigator on how to obtain treatment assignment in the event of an emergency unblinding. The Investigator is requested to contact the Medical Monitor promptly in case of any treatment unblinding. If a subject's treatment assignment is unblinded, the Sponsor must be notified within

24 hours after breaking the blind. The date and reason the blind was broken must be recorded in the source documentation and electronic case report form (eCRF), as applicable.

For Suspected, Unexpected, Serious Adverse Reactions, the Sponsor's Pharmacovigilance designee responsible for managing SAEs, will access the IWRS to obtain the subject's treatment assignment for the purpose of regulatory reporting.

If a subject's treatment assignment is unblinded prior to Week 12 for any reason, they will be discontinued from the study. Subjects who are unblinded on or after Week 12 may be eligible to enroll into the OLE study (Section 5.1.1).

